5.2. Determination of Sample Size

Approximately 1899 patients will be randomized to achieve approximately 1424 patients who will complete the Placebo-Controlled period.

This sample size has been calculated to provide at least 90% power to detect a treatment difference in a key functional secondary outcome, that is, the change in ADCS-iADL at 78 weeks. Based on estimates of treatment change and standard deviation from the mild APOE4 carriers (APOE4 used as a surrogate for amyloid positivity to more closely correspond to the patient population to be enrolled in this study) in the pooled solanezumab studies LZAM/LZAN, an expected mean change (SD) in ADCS-iADL score is 2.07 (9.78) which equates to an effect size of 0.212.

A total of 554 patients completing the study per arm would be required to provide 90% power at $\alpha = 0.025$. Assuming a 25% dropout rate and a 50% information rate for dropouts, 633 (554/(1-0.25%*50%)) patients will need to be randomized per arm (633 in combined placebo arms during the Placebo-Controlled period). This equates to a total randomized sample size of 1899.

This calculated sample size provides greater than 90% power to evaluate the primary outcome for the Placebo-Controlled period. Based on estimates of treatment change and standard deviation from the mild APOE4 carriers in the pooled solanezumab studies LZAM/LZAN, an expected mean change (SD) in ADAS-Cog13 is 2.91 (10.84), corresponding to an effect size of

0.269. A total of 633 patients randomized per arm will yield over 99% power for this analysis. Additionally, 554 patients completing the study per arm would provide over 98% power.

Using the three stage hypothesis testing approach to delayed start analysis, as outlined in Liu-Seifert and colleagues (2015), this sample size will provide approximately 80% power at an alpha level of 0.1 for each dose when all patients have the opportunity to reach the 6 month time point of the Delayed-Start period. At the 18 month time point of the Delayed-Start period, this sample size will provide approximately 50% power. At the time of submission based on current enrollment projections, it is forecasted that 33-40% of patients will not have had the opportunity to reach the 6-month time point. Accounting for this decreased sample size at the time of submission, the power of this Delayed Start analysis is reduced from 80% to approximately 75%.

These power calculations are based on the delayed-start results from the pooled solanezumab studies LZAM/LZAN among APOE4 carriers. Treatment differences at the end of the Placebo-Controlled and Delayed-Start periods and the corresponding variance and covariance estimates were used to calculate the power empirically. For the 6 month time point of the Delayed-Start period, the assumed early discontinuation (EDC) rate used for these calculations was 30%, and 40% for the 18 month Delayed-Start time point. These EDC assumptions were used to adjust the randomized sample sizes using the following formula:

Effective Sample Size = (Randomized Sample Size) * (1 - 0.50*EDC)

The effective sample size assumes that EDC patients will contribute half the information that completing patients contribute. The effective sample sizes for the 6 month power calculation were 531 and 266, early-start arm and delayed-start arm, respectively; for 18 months, 500 and 250, early-start arm and delayed-start arm, respectively.

5.3. Method of Assignment to Treatment

Patients who meet all criteria for enrollment will be randomized at Visit 2. Assignment to treatment groups will be determined by a computer-generated random sequence using an interactive web-response system (IxRS). The IxRS will be used to assign the package containing double-blind investigational product to each patient. Site personnel will confirm that they have located the correct package by entering a confirmation number found on the packages into the IxRS.

To achieve between-group comparability for site, the randomization will be stratified by site.

This is a double-blind study, with a Placebo-Controlled period and a period without placebo (Delayed-Start period). Both patients and site personnel are to remain blinded to dose and prior allocation of placebo throughout the study.

To preserve the blinding of the study, a minimum number of Lilly personnel will see the randomization table and treatment assignments before the study is complete.

Controlled and Delayed-Start periods, placebo followed by LY3314814 20 mg, or placebo followed by LY3314814 50 mg in a ratio of 2:2:1:1. If a subject withdraws from the study, the subject's screening and randomization code will not be reused, and the subject will not be allowed to reenter the study. The IxRS will be used to assign a dosing regimen to each patient.

6. A Priori Statistical Methods

6.1. General Considerations

For treatment group comparisons of the Placebo-Controlled period, the two placebo treatment groups (Placebo-20 mg and Placebo-50 mg) will be pooled to form one placebo-treated control group. This group will be labelled as the placebo treatment group (PLA) in presentations summarizing the Placebo-Controlled period.

As the study was stopped for futility, the planned statistical tests lose their scientific validity and multiplicity is no longer a concern. All reported p-values will not be adjusted for multiplicity. No test will be interpreted as statistically significant, and tests resulting with low p-values will only be considered as potential results of interest.

All analyses will follow the intention-to-treat (ITT) principle unless otherwise specified. An ITT analysis is an analysis of data by the groups to which subjects are assigned by random allocation, even if the subject does not take the assigned treatment, does not receive the correct treatment, or otherwise does not follow the protocol.

6.1.1. Placebo-Controlled Period

Data summaries will include a total column and columns describing the treatments received only in the Placebo-Controlled period: 20mg, 50mg, or PLA. When change from baseline is assessed, subjects will be included in the analysis only if both a baseline and a post-baseline measurement are available. Unless otherwise defined, a baseline measurement is the last non-missing observation collected during Visits 1 and 2. End point is the last non-missing post-baseline measurement prior to the Delayed-Start period. For analyses using last observation carried forward (LOCF), the last non-missing post-baseline measurement (scheduled or unscheduled) will be used to calculate change from baseline. With the early termination of this study, all results are considered to be suggestive or hypothesis-generating rather than the originally planned confirmatory interpretation of the test or comparison.

6.1.2. Delayed-Start Period

Unless otherwise defined, a baseline measurement is the last non-missing observation collected prior to the Delayed Start period. No between treatment p-values will be reported because (1) all patients received active treatment in the Delayed Start period, and (2) previous treatments in the Placebo-Controlled period were randomized at baseline and do not guarantee patients entering the Delayed Start period are without selection bias. Data summaries will include a total column and columns describing the treatments received across both study periods: 20mg, 50mg, PL/20 and PL/50.

When change from baseline is assessed, subjects will be included in the analysis only if both a baseline and a post-baseline measurement are available. Endpoint is the last non-missing post-baseline measurement. For analyses using last observation carried forward (LOCF), the last non-missing post-baseline measurement (scheduled or unscheduled) will be used to calculate change from baseline.

6.2. Adjustments for Covariates

Repeated measures models will include the fixed, categorical effects of treatment, visit (treated as a categorical variable), treatment-by-visit interaction, pooled site, and concomitant AChEI and/or memantine use at baseline (yes/no), as well as the continuous, fixed covariate of baseline, baseline-by-visit interaction and age at baseline.

When an analysis of covariance (ANCOVA) model is used to analyze a continuous efficacy or safety variable, the model will contain the main effects of treatment, pooled site, concomitant AChEI and/or memantine use at baseline (yes/no), and the appropriate baseline value as a covariate.

6.3. Handling of Dropouts or Missing Data

6.3.1. Handling Missing Data from Subject Dropouts

A likelihood-based mixed effects model for repeated measures will be used to handle missing data. The model parameters are simultaneously estimated using restricted likelihood estimation incorporating all of the observed data. Estimates have been shown to be unbiased when the missing data are missing at random and when there is ignorable non-random missing data.

Repeated measures analyses will only use data from visits where the data was scheduled to be collected (see Andersen and Millen 2013). When subjects discontinue from the study early, there may be efficacy or safety data measurements at visits where the variables were not scheduled to be collected. These data will be used in all other analyses.

6.3.2. Handling Missing Items in Calculating Totals

All total and subscale scores for safety, efficacy, and health outcomes measures will be derived from individual items. If any of the individual items are missing or unknown, every effort will be made to obtain the score for the missing item or items.

For ADAS-Cog13, if <30% (4 or fewer of a total of 13 items) of the items are missing, the total score (maximum = 85) will be imputed as follows: The total from remaining items will be multiplied by a factor that includes the maximum score for the missing items. For example, if the first item, "Word-Recall Task," which ranges from a score of 0 through 10 (maximum = 10) is missing, and the second item "Commands," which ranges from a score of 0-5 (maximum = 5) is missing then the multiplication factor = 85/(85 - [10 + 5]) = 85/70 = 1.21. Thus, the total score for this example will be the sum of the remaining 11 items multiplied by 1.21. The imputed number will be rounded up to the nearest integer. If more than 4 items are missing, the total score for ADAS-Cog13 at that visit will be considered missing. The same imputation technique will be applied to any other ADAS-Cog subscore, if tested.

For the FAQ and ADCS-iADL, if 30% or fewer of the items are missing, the total score will be imputed. The sum of the nonmissing items will be prorated to the sum of total items. The imputed number will be rounded up to the nearest integer. If the nearest integer is greater than

the maximum possible score, the imputed score will be equal to the maximum score. If >30% of the items are missing, the total score at that visit will be considered missing.

The same imputation technique will be applied to the ADCS-ADL total score. Note that, depending on the specific item responses that are missing, it is possible to have an imputed total score for both the ADCS-iADL and the ADCS-ADL, an imputed total score for one but not the other, or both total scores missing.

The same imputation technique will be applied to the CDR-SB. If only 1 box (of 6) of the CDR is missing, the sum of the boxes will be imputed by prorating the sum from the other 5 boxes. If the score from more than 1 box is not available, the CDR-SB at that visit will be considered missing.

For the RBANS, if <30% of the sub-items are missing (ie, no more than 3 of the 12 sub-items), the item score will be imputed. For the missing subtest, the scaled score from the other subtest within that index will be used to impute the missing scaled score, which is then converted to a raw score. If List Recognition is missing, the scaled score mean for List Recall, Story Recall, and Figure Recall should be used to impute the missing value. If two sub items are missing within the same index and/or if >30% of the sub-items are missing, the total score for the RBANS at that visit will be considered missing. For all other scales, if any item is missing, any total or sum involving that item will be considered missing.

6.4. Multicenter Studies

This study will be conducted by multiple investigators at multiple sites internationally. A listing will be prepared including country, investigator site with address, number of subjects enrolled (randomized) by each site and unique subject ID.

Sites with fewer than 6 evaluable patients (see Section 6.6.) will be pooled for the statistical analysis. All sites with fewer than 6 evaluable patients on the primary endpoint will be pooled within country and considered as a single site for analysis. If this results in a pooled site still having fewer than 6 evaluable patients, this site will be pooled together with the next smallest site, if one exists, in that country; otherwise, no further pooling is needed. These pooled sites will be used for any analysis that has site as a fixed effect in the model. The actual site numbers will be included in the listings.

6.5. Multiple Comparisons/Multiplicity

As the study was stopped for futility, multiplicity is no longer a concern. All reported p-values will not be adjusted for multiplicity.

6.6. Analysis Populations

For purposes of analysis, populations are defined in Table AZET.SAP.1.

Table AZET.SAP.1. Analysis Populations for Study I8D-MC-AZET

Population	Description	
Entered	All participants who sign informed consent	
Randomized	All entered patients who are randomized to study treatment.	
Evaluable – PC	All randomized patients with a baseline and at least one post-baseline scale result; only placebo-controlled visits included $(1-16)$	
Safety – PC	All randomized participants who take at least 1 dose of double-blind study treatment. Participants will be analyzed according to the treatment group to which they were randomized. Only placebo-controlled visits included $(1-16)$	
Safety – DS	All randomized participants who take at least 1 dose of double-blind study treatment. Participants will be analyzed according to the treatment group to which they were randomized. All visits included $(1-30)$	

Abbreviations: PC = Placebo-Controlled; DS = Delayed-Start

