AZET (The DAYBREAK Study) is a randomized, double-blind, placebo-controlled study of LY3314814 in patients with mild Alzheimer's Disease (AD) dementia and abnormal levels of amyloid, consisting of a 78 week Placebo-Controlled period followed by a 78 week Delayed-Start period. Study AZET was deemed to be futile and stopped on June 12, 2018. Because of this futility, the original planned delayed-start analysis of evaluating disease modification of LY3314814 by summarizing both efficacy and safety across both study periods became moot. Analyses of study AZET will be separated by study period: placebo-controlled study period and the delayed start study period.

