6.13. Safety Analyses

Safety presentations will be based on the Safety-PC and Safety-DS populations, as relevant. No between treatment p-values will be calculated for analyses of the Safety-DS population.

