6.13.1. Extent of Exposure

Days of exposure will be calculated for each subject: (Date of last dose – date of first dose + 1). Summary statistics will be presented for the total number of days of exposure by treatment. Study drug treatment assignment will be listed.

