6.13.2. Adverse Events

Adverse events will be summarized and compared across treatment groups in the Placebo-Controlled period and the entire study. Treatment-emergent adverse events (TEAEs) will be defined as those events that first occurred or worsened after the date of randomization (Visit 2).

Should there be insufficient data to make this determination (i.e., missing or incomplete AE start date, stop date, or time), the AE will be considered treatment-emergent. The treatment-emergent period ends on the last day of treatment plus 5 days (these 5 days constitute at least 5 half-lives of lanabecestat). Events occurring within the study but during a period of treatment interruption will only be treated as treatment-emergent if they occur within 5 days of the last dose prior to the treatment interruption.

The MedDRA lower-level term (LLT) will be used in the treatment-emergent computation. The maximum severity for each lower-level term (LLT) during the baseline period will be used as baseline.

An overview of AEs, including the number and percentage of patients who died, suffered serious adverse events (SAEs), discontinued due to AEs and who suffered TEAEs, will be provided. Comparison between treatments will be performed using Fisher's Exact Test.

Summaries of AEs by decreasing frequency of PT within SOC will be provided for the following:

- Preexisting condition
- TEAEs
- TEAEs by maximum severity
- TEAEs occurring in at least 2% of subjects by preferred term
- Serious AEs
- AEs reported as reason for study treatment discontinuation

These summaries will include number and percentages of subjects experiencing the events. Treatment comparisons will be carried out using Fisher's Exact Test. For TEAEs by maximum severity, Severity ="Severe" and "More Severe" will be combined into "Severe" category and the treatment comparison will be performed using Fisher's Exact Test.

All reported preexisting conditions and adverse events (with designations for TEAEs, SAEs, and discontinuations due to AEs) will be listed.

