6.13.3. Deaths, Other Serious Adverse Events, and Other Notable Adverse Events

Overviews of adverse events will be presented for the Placebo-Controlled period and the Delayed-Start period, respectively, including within each period the number and percentage of subjects who died, experienced serious adverse events, experienced adverse events leading to study discontinuation, and experienced treatment-emergent adverse events. Treatment groups will be compared in the Placebo-Controlled period using Fisher's Exact Test.

Events of the major adverse cardiovascular event type (MACE) that are blindly evaluated by external independent consultants will be summarized and listed.

In addition, the proportion of subjects within specific clusters of TEAEs will be summarized and treatment comparisons will be conducted using Fisher's Exact Test. Clusters will be created from MedDRA High Level Group Terms (HLGTs) and MedDRA SMQ's.

 Table AZET.SAP.2.
 Adverse Events of Special Interest

AE Groups of Interest (Clusters)	MedDRA High Level Group Terms (HLGTs)
Nervous System Disorders	Neuromuscular Disorders HLGT
	Demyelination SMQ
	Peripheral Neuropathy SMQ
Eye Disorders	Retinal disorders SMQ
Skin Disorders	Sub-group A:
	Epidermal and Dermal Conditions HLGT (excluding sub-group B terms)
	Sub-group B (Hypopigmentation-related events):
	Hypopigmentation disorders HLT
	Pigmentation changes, NEC HLT
	Preferred terms: 'hair depigmented', 'eyelash discolouration', 'iris hypopigmentation', 'eye colour change', 'lip colour altered', 'lip discolouration', 'hair colour changes', 'achromotrichia aquired', 'poliosis'
Liver Disorders	Drug related hepatic disorders - comprehensive search SMQ
Cardiovascular-type events – Arrhythmic	Arrhythmia related investigations, signs and symptoms SMQ
	Cardiac arrhythmia terms (incl bradyarrhythmias and tachyarrhythmias) SMQ
	TdP/QT prolongation SMQ
Cardiovascular-type events - Ischemic	Ischaemic heart disease SMQ
Cardiovascular-type events - Stroke	Central nervous system vascular disorders SMQ
Cardiovascular-type events – including orthostatic hypotension	Decreased and Nonspecific Blood Pressure Disorders and Shock HLGT

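### Safety-DS includes patients never dosed in the Delayed-Start period, so it suits the entire-study tables but is the wrong denominator for the within-period overview in SAP 6.13.3

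*SAP*

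**What the plan says.** SAP 6.6 (Table AZET.SAP.1) defines two safety populations. Both take in anyone randomized who received one dose or more, grouped as randomized. Safety-PC covers visits 1 to 16. Safety-DS places patients in the group "to which they were randomized. All visits included" (1 to 30).

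SAP 6.13 offers no other set: "Safety presentations will be based on the Safety-PC and Safety-DS populations, as relevant".

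Two adverse-event outputs draw on these sets:

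- SAP 6.13.2 summarizes events "in the Placebo-Controlled period and the entire study". Treatment-emergent events are "those events that first occurred or worsened after the date of randomization".
- SAP 6.13.3 asks for a separate overview of each period, "including within each period the number and percentage of subjects who died", together with serious events, discontinuations due to adverse events, and treatment-emergent events.

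Three other statements bear on the point:

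- SAP 6.1.2 sets a separate Delayed-Start baseline, specifies four columns (20mg, 50mg, PL/20, PL/50), rules out between-treatment p-values, and acknowledges that patients who go on to this period may be a selected group.
- SAP 6.12.2.1 says that only a small number of patients were exposed in the period, and that safety is all that will be summarized from it.
- SAP 4 gives the reason: "Study AZET was deemed to be futile and stopped on June 12, 2018".

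**The concern.** A percentage of patients with an event within a period needs a denominator of patients who could have had the event in that period. No population in the table requires a dose, or even a visit, after Week 78. Applied as written, the rule puts patients who left during the first 78 weeks, or were still in them when the study stopped, into the Delayed-Start denominator.

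The numerator is also open. Safety-DS spans visits 1 to 30 and treatment emergence runs from randomization. A programmer following those two rules could count first-period events, including events on placebo in the PL/20 and PL/50 columns, in a table headed Delayed-Start.

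At stake is how the Delayed-Start percentages for deaths, serious events, discontinuations and treatment-emergent events are read. For former placebo patients this is the first time on active drug.

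**Working it through.** **1. Membership against need**

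| Output | Needs | Safety-DS supplies |
|---|---|---|
| 6.13.2, entire study | everyone dosed, all visits | this: it fits |
| 6.13.3, Delayed-Start overview | patients dosed in that period, events in that period | everyone dosed at any time, all visits: it does not fit |

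**2. The plan's own figure.** SAP 5.2: "Approximately 1899 patients will be randomized to achieve approximately 1424 patients who will complete the Placebo-Controlled period". Protocol 5.2 assumes 25% discontinuation. 1899 × (1 − 0.25) = 1424.25, which reproduces 1424. Planned completion is 1424/1899 = 0.750.

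**3. Formula, if events are limited to the period.** Let a column have n patients in Safety-DS, of whom m entered the Delayed-Start period and e had an event there. Then

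displayed = e/n = (m/n) × (e/m) = p × percentage among patients at risk.

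**4. Who could have entered.** Entry comes at Week 78, or 546 days. Counting back from 12 June 2018 gives 13 December 2016. With the 7-day visit window (539 days) it is 20 December 2016. Assuming nobody started Delayed-Start dosing after the stop, only patients randomized by about then could contribute. If s is the share randomized by that date (not stated) and completion was as planned, p = 0.75 × s. So p reaches 75% only when s = 100%. Nearly all randomized patients are taken to have been dosed.

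**5. Size.** Dose column of 1899/3 = 633 and an assumed true percentage of 20%. The rows for p = 25% and 10% are also assumptions.

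| p | s = p/0.75 | Entrants | Events | Displayed (events/633) | Exact 95% interval among entrants |
|---|---|---|---|---|---|
| 75% | 100% | 475 | 95 | 15.0% | 16.5–23.9% |
| 25% | 33% | 158 | 32 | 5.1% | 14.3–27.4% |
| 10% | 13% | 63 | 13 | 2.1% | 11.5–32.7% |

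PL/20 and PL/50 would hold about 1899/6 = 316.5 patients each. The same p gives the same dilution there on half the numbers.

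**6. Columns need not share p.** With an assumed 10% risk in two columns and entry of 12% and 8%, the table would show 0.12 × 10% = 1.2% and 0.08 × 10% = 0.8%, although the risk is equal.

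**7. If events are not limited.** The formula in step 3 no longer applies. The numerator gains first-period events, so the result is a cumulative percentage under a Delayed-Start label. The documents give no event rates from which to size this.

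**The case against.** The best defence is that the phrase in 6.13.3 about each period already limits the denominator, that 6.13 lets the relevant set be chosen, and that 6.1.2 plainly has in mind patients who enter the period. On that reading a sensible programmer would use entrants only. This shows what was probably intended, but it does not define the set. 6.13 chooses between two populations, and neither is limited to entrants. Elsewhere the plan states its filter: 6.1.2 requires a baseline and a post-baseline value for change analyses, and 6.13.4 and 6.13.5 do so for laboratory and vital-sign proportions. The adverse-event overview has no such filter.

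Other parts of the defence stand, and they rule out stronger readings that a reader might infer:

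- *All Delayed-Start percentages are too low by one common factor.* The direction depends on the numerator being limited to the period, which the SAP leaves open. The factor also belongs to each column.
- *This overview is the only account of deaths, serious events and discontinuations in the period.* 6.13.2 gives an entire-study overview, tables of serious events and of events leading to discontinuation, and full listings. Counts appear beside percentages and do not depend on the denominator.
- *The randomization anchor for treatment emergence and the single-first-dose exposure formula are errors.* The anchor is right for the entire-study tables. No Delayed-Start exposure table is promised, so "Days of exposure will be calculated for each subject" contradicts nothing.

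**Conclusion.** The point holds for the 6.13.3 Delayed-Start overview, and for any other within-period Delayed-Start percentage without a baseline-plus-postbaseline filter. It is minor. Following the stated populations gives either a diluted percentage or a mixed-period one, depending on how events are windowed.

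Under dilution, at least a quarter of the denominator is not at risk even at planned completion. SAP 6.12.2.1 suggests that the true share is much larger. The actual p is not in the documents, so the 25% and 10% cases and the 20% event rate only show scale.

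Safety-DS itself is not wrong. It is a sound entire-study population under a misleading label. Entire-study tables, listings and Safety-PC comparisons are unaffected, and no Delayed-Start p-values are planned. The documents do not support any claim that a treatment comparison is biased or that safety events go unreported.

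**What to change.** - **Keep Safety-DS**, relabelled as the entire-study safety population, for 6.13.2 and for cumulative tables such as disposition (6.7) and skin findings (6.13.8.2).
- **Add one population:** randomized patients with at least one dose in the Delayed-Start period. Use it as the denominator for the 6.13.3 Delayed-Start overview and for other within-period percentages that lack the baseline-plus-postbaseline filter.
- **Add one event-window sentence:** the Delayed-Start overview counts events that first occur or worsen on or after the first Delayed-Start dose.
- **Optional:** an exposure summary counted from that dose.

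The cost is one table row, one sentence and one programming flag. Denominators shrink and precision falls, as the intervals above show. The group is selected by completing the first period, so its percentages should stay descriptive. In the early-start columns the drug does not change at Week 78, so an event that began earlier on the same dose would count only if it worsened. The new table should therefore be read beside the entire-study tables.
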